3.2. General Considerations

Continuous data will be summarized using the number of observations (n), arithmetic mean (mean), SD, median, minimum value (min), and maximum value (max) by treatment group. Categorical variables will be summarized using the frequency count (n) and percentage (%) by treatment group. For all percentage calculations, the denominator will be the number of subjects in the population for the treatment group, unless otherwise stated. An overall/total group (i.e., a sum of all treatment groups) will generally be presented additionally for summaries of disposition, demography, and baseline characteristics. Biomarker and PK endpoints will be summarized using geometric means and SDs as appropriate.

The data from Stage 2 and Mild Stage 3 groups will be analyzed overall and separately for the Stage 2 and Mild Stage 3 groups, which aims to provide a comprehensive understanding of the study outcomes for each group.

In instances where unscheduled or early termination visits occur, these visits will be mapped into the corresponding scheduled visits when appropriate. This approach ensures that all relevant data is included in the analysis and provides a comprehensive evaluation of the study parameters.

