2.3. Safety Population

The safety population will include all randomized subjects who receive at least 1 dose of the study drug, with subjects grouped according to the treatment they receive. This population will be used in all safety analyses with subjects analyzed according to the actual treatment they receive. If subjects receive a different treatment from the one they were randomized to throughout the entire study, they will be analyzed according to the different treatment received. However, subjects who receive mixed treatments due to dosing errors will be analyzed according to their randomized treatment.

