6.2. Laboratory Values

Blood samples for hematology, clinical chemistry, and urinalysis will be collected at the visits defined in protocol and the test results will be presented in standard units. The continuous test results and change from baseline will be descriptively summarized by visit and treatment group. Laboratory parameters that will be assessed will include:

- Hematology: hemoglobin, hematocrit, red blood cell count (RBC), platelet count, white blood cell count (WBC), WBC differential, neutrophils, eosinophils, monocytes, basophils, and lymphocytes
- Clinical chemistry: albumin, alkaline phosphatase, alanine aminotransferase, aspartate aminotransferase, bicarbonate, total bilirubin, direct bilirubin, indirect bilirubin, calcium, chloride, total cholesterol, creatinine, gamma-glutamyl transpeptidase, glucose, high-density lipoprotein, low-density lipoprotein, lactate dehydrogenase, potassium, sodium, total protein, triglycerides, urea, and uric acid
- Urinalysis: albumin, bilirubin, erythrocytes, glucose, ketones, leukocyte, microscopy, nitrite, pH, specific gravity and urobilinogen
- Coagulation: PT (sec), PT (INR), aPTT

Clinical laboratory test results will be assigned a Low/Normal/High (L/N/H) classification according to whether the value is below (L), within (N), or above (H) the laboratory parameter's reference range. Shifts from baseline to each post-baseline visit will be provided for each laboratory parameter by treatment group.

Abnormal laboratory test results (i.e., results assigned as L/H) will be listed in a by-subject data listing.

CSF assessments, which include WBC, RBC, protein, and glucose, will be gathered locally. These measurements will subsequently be converted to standard units. The test results for WBC and protein will be descriptively summarized by visit and treatment group.

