6.5. Physical Examination

Abnormal physical examination results will be listed in a by-subject listing.

6.6. 12-Lead Electrocardiogram (ECG)

The ECGs parameters (including heart rate, RR interval, PR interval, QRS interval, QT interval, Corrected QT interval using Bazett's formula [QTcB] and Corrected QT interval using Fredericia's formula [QTcF]) and the change from baseline will be summarized descriptively by visit and treatment group. The ECGs will be performed in triplicate. For the above ECG parameters, the averaged value of the triplicate will be used for the analysis. For the overall interpretation of ECG (normal, abnormal clinically significant, or abnormal not clinically significant), the value that represents the greatest degree of abnormality will be used for the analysis. In addition, shift from baseline to each post-baseline visit in the overall interpretation will be provided by treatment group.

Categorical analysis of the maximum post-baseline value in QTcF interval will be performed to summarize the number and percentage of subjects meeting the criteria below.

- Absolute QTcF interval prolongation:
 - QTcF interval \leq 450 ms
 - QTcF interval > 450 and ≤ 480 ms
 - QTcF interval > 480 and ≤ 500 ms
 - QTcF interval > 500 ms
- Change from baseline in QTcF interval:
 - QTcF interval increases from baseline ≤ 30 ms
 - QTcF interval increases from baseline > 30 and ≤ 60 ms
 - QTcF interval increases from baseline > 60 ms

A by-subject listing of ECG results will be provided.

[figure not shown]

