6.8. Columbia Suicide Severity Rating Scale (C-SSRS)

The Columbia-Suicide Severity Rating Scale (C-SSRS) is a measure used to identify and assess individuals at risk for suicide. The C-SSRS summary will display the number and percentage of subjects who report “Yes” to specific C-SSRS items or categories of items (a category is assigned a “Yes” value if a “Yes” is reported for any item in the category) descriptively by visit and treatment group. These C-SSRS items and categories are as follows:

- Suicidal Ideation Items
 - (1) Wish to be dead
 - (2) Non-specific active suicidal thoughts
 - (3) Active suicidal ideation with any methods (not plan) without intent to act
 - (4) Active suicidal ideation with some intent to act, without specific plan
 - (5) Active suicidal ideation with specific plan and intent
- Suicidal Behavior Items (not reported for the Screening/past 1 year assessment)
 - (6) Preparatory acts or behavior
 - (7) Aborted attempt
 - (8) Interrupted attempt
 - (9) Non-fatal suicide attempt
 - (10) Completed suicide
- Suicidal Behavior Category: Any of items (6) through (10)
- Non-Suicidal Self-Injurious Behavior

In addition to the summaries described above, the shift from baseline to each post-baseline visit in suicidal ideation and behavior (categorized as (1) No Suicidal Ideation or Behavior, (2) Suicidal Ideation only, and (3) Suicidal Behavior will be provided by visit and treatment group.

The C-SSRS results will be provided in by-subject data listings.

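### With no by-visit denominator stated, the SAP's default rule counts a missing C-SSRS as a 'No' and lowers the printed percentages in proportion to missing assessments

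*SAP*

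**What the plan says.** SAP 3.2 gives the format for categorical data, "Categorical variables will be summarized using the frequency count (n) and percentage (%) by treatment group", and then the denominator: "For all percentage calculations, the denominator will be the number of subjects in the population for the treatment group, unless otherwise stated". Safety tables use the Safety Population of SAP 2.3: "The safety population will include all randomized subjects who receive at least 1 dose of the study drug". Membership does not require a post-baseline assessment.

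Three safety sections contain categorical tables, and none states its own denominator or a missing category:

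- **C-SSRS (SAP 6.8).** "The C-SSRS summary will display the number and percentage of subjects who report" a 'Yes', presented "descriptively by visit and treatment group. These C-SSRS items and categories are as follows". A by-visit shift table follows.
- **ECG (SAP 6.6).** There are two tables. For the normal/abnormal reading, "shift from baseline to each post-baseline visit in the overall interpretation will be provided by treatment group". The QTcF thresholds are applied to each subject's maximum post-baseline value, "to summarize the number and percentage of subjects meeting the criteria below".
- **Laboratory (SAP 6.2).** "Shifts from baseline to each post-baseline visit will be provided for each laboratory parameter by treatment group". Percentages are not mentioned here; they would follow only from the general rule in 3.2.

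Two other rules matter. SAP 3.4.8 says missing safety data are not imputed. SAP 3.4.6 applies the analysis visits to by-visit safety summaries and drops any assessment later than 30 days after the last dose. SAP 7 places the table shells in a separate document.

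**The concern.** Safety against placebo is a primary objective, and C-SSRS is a named safety endpoint. At a late visit the Safety Population includes people who stopped treatment, missed the visit, or were assessed outside the 30-day limit. Under the default rule all of them remain in the denominator of the 'Yes' percentage. That has the same effect as recording 'No' for each, which sits badly with the statement that safety data are not imputed.

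The 30-day limit sharpens the point. Protocol 4.4 expects evaluations to continue on schedule after study drug is stopped. A late 'Yes' from such a subject would be removed from the numerator while the subject stayed in the denominator.

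These tables are descriptive, so the printed percentage is what the reader uses. If one arm has more missing assessments than another, the comparison between arms shifts in favour of the arm with more missing.

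**Working it through.** The documents state no C-SSRS rate, by-visit missing rate or dropout rate, so there is no figure to reproduce.

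**Inputs.** The denominator rule is from SAP 3.2 and the population from SAP 2.3. For arm size, SAP 1.1 plans about 144 subjects in Parts A, B, D and E, split 1:1 between doses and 2:1 active to placebo within each Part. That gives 144/2 × 2/3 = 48 on each dose and 144 × 1/3 = 48 on placebo. Event counts and missing shares are assumptions.

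**Formula.** Let N be the Safety Population of the arm, m the share with no usable assessment at the visit, and e the number with a 'Yes'.

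- Rate among assessed = e / [N(1 − m)]
- Printed under SAP 3.2 = e / N = (rate among assessed) × (1 − m)

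**One arm, N = 48, e = 5** (the non-integer denominators are for illustration):

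| Assumed missing | Printed | Among assessed |
|---|---|---|
| 10% | 5/48 = 10.4% | 5/43.2 = 11.6% |
| 20% | 10.4% | 5/38.4 = 13.0% |
| 30% | 10.4% | 5/33.6 = 14.9% |

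**Two arms, same rate among assessed.** The ratio of printed rates, active to placebo, is (1 − m_active)/(1 − m_placebo):

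- 10% v 5% missing: 0.90/0.95 = 0.95
- 20% v 5% missing: 0.80/0.95 = 0.84
- 30% v 5% missing: 0.70/0.95 = 0.74
- equal missingness: 1, so the ratio is unchanged

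**Whole-number case.** Take 48 per arm and 4 events in each, with 12 missing on active and 3 on placebo. The default prints 4/48 = 8.3% in both arms. Among those assessed the rates are 4/36 = 11.1% and 4/45 = 8.9%.

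**Other tables.**

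- *Shift tables.* A missing post-baseline value enters no cell. If percentages are printed over N, every cell, normal and abnormal, is multiplied by (1 − m), where m now counts subjects lacking either value. The cells then sum to 100 × (1 − m)%, for example 80% when 20% are missing.
- *Maximum QTcF.* A subject who stops late still contributes earlier ECGs. The denominator problem is confined to subjects with no usable post-baseline ECG.

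**The case against.** The strongest objection is that the rule is only a default and the shells were not available. They may already use the number assessed at each visit. That stands: the documents show that the SAP text has no exception, not what the tables will print.

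There are also mitigations. Counts are printed beside percentages. By-visit continuous ECG and laboratory summaries show the number of observations. Abnormal laboratory results, ECGs and C-SSRS results are listed by subject. Early termination visits are mapped to analysis visits where they fall in a window. These let a careful reader recover much of the information. For C-SSRS, though, no continuous summary shows how many were assessed.

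It is also fair to say that the observed-case rate is not the true rate. If subjects with suicidality or abnormal findings are the ones who stop, it too can be biased. This stands, and is why the fix asks for the number missing as well as a new denominator.

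A reader might infer three stronger things that the documents do not support:

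- *Missing ECG or laboratory values are counted as normal.* They are not. In a shift table they fall in no cell.
- *Late dropout dilutes the QTcF categories in the same way.* It does not, because that table is not by visit.
- *The plan makes the active doses look safer.* That needs more missing data on active than on placebo, and nothing in the documents shows this.

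**Conclusion.** The point holds for the by-visit C-SSRS 'Yes' percentages. Followed as written, SAP 3.2 and 6.8 print the rate among those assessed multiplied by (1 − share missing). With 48 subjects and 5 events, that is 10.4% in place of 11.6% to 14.9% for 10% to 30% missing. It holds in a weaker form for ECG and laboratory shifts, if percentages are printed: cells shrink and totals fall below 100%. It barely touches the maximum QTcF categories.

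The size rests on assumed missing shares and event counts. Distortion between arms also requires unequal missingness. The conclusion assumes that the shells state no other denominator. Because the tables are descriptive, no test, estimand or sample size is affected. This is a minor-to-moderate reporting correction.

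**What to change.** Add to SAP 3.2, and carry into the shells, these denominators:

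- By-visit percentages: subjects with a non-missing assessment at that visit.
- Shift tables: subjects with both a baseline value and a value at that visit.
- Maximum post-baseline categories: subjects with at least one post-baseline value.
- Adverse events, medical history and disposition: the population N, as now.

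Print the denominator and the number missing, by arm, in each of the first three kinds of table, so that readers can judge whether dropout may be hiding events. If the shells already do this, the SAP sentence only needs to match them.

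The cost is a short addition to the SAP and an edit to the shells. Denominators will then vary by visit. No new data or analyses are needed.

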3.3. Interim Analysis

An interim analysis was conducted in June 2023 to confirm the PK and PD expectations and to evaluate safety after approximately 36 subjects in Stage 2 have completed 12 weeks of treatment. Subsequently, in June 2024, an update of interim analysis was conducted when these subjects completed 12 months of treatment. The interim analyses included only descriptive summaries of PK, PD, clinical efficacy and safety endpoints. Since the interim analyses followed the same procedures as the DSMB, the analysis details were outlined in the DSMB SAP.

An independent analysis team conducted the unblinded analysis. Only summary level results were shared with the PTC study team. The study has maintained double-blinding for investigators and the sponsor study team at a subject level until after the database is locked.

3.4. Data Definitions and Analysis Issues

3.4.1. Study Day

The study day will be defined as the number of days since the randomization day, which is assigned as Day 1 of the study. The study day is calculated using the formula if the assessment date is on or after the date of randomization:

$$\text{Study day} = (\text{Date of assessment} - \text{Date of randomization}) + 1$$

Otherwise, if the assessment date is before the date of randomization, then the study day will be calculated as follows:

$$\text{Study day} = \text{Date of assessment} - \text{Date of randomization}$$

3.4.2. Baseline Definitions and Change from Baseline

For all efficacy and PD endpoints, unless otherwise specified, the assessments collected at the randomization date will serve as the baseline value. If the randomization visit value is not available, then the last non-missing assessment collected prior to randomization will serve as the baseline. For safety endpoints, the baseline value is defined as the last non-missing assessment prior to the first study drug administration.

For the analysis purposes, change from baseline and percent change from baseline will be derived as follows:

$$\text{Change from baseline} = \text{Post-baseline value} - \text{Baseline value}$$

$$\text{Percent change from baseline} = 100 \times (\text{Post-baseline value} - \text{Baseline value}) / \text{Baseline value}$$

For the vMRI assessments, where the change is directly measured using the Boundary Shift Integral (BSI) for multiple brain areas, the change will not be calculated. For more details, please refer to Section [3.4.3](#).

3.4.3. Volumetric Magnetic Resonance Imaging

The loss of brain tissue is a continuous variable of disease progression in HD. Volumetric Magnetic Resonance Imaging (vMRI) will be used to effectively assess potential changes in brain volume (whole brain, lateral ventricles, caudate, and putamen volumes) to help determine if the treatment affects the rate of volume loss.

The vMRI images will be used to detect changes in brain volume in different areas over time using the boundary shift integral (BSI) technique. The BSI technique uses the shift in intensity differences on a pair of registered intensity-normalized images to quantify the difference between the 2 images (i.e., to quantify the amount of change in those selected brain regions). This technique is considered the gold standard to measure global brain or regional atrophy (tissue loss) and the output of BSI method is the change from baseline in volume (atrophy or expansion) over time.

The following regional brain volumes and measurements of volume change over time will be assessed at Visit 2 (Baseline) and Visits 5 (Month 3) and 8 (Month 12) in the six brain regions listed below:

- Whole Brain
- Lateral Ventricle
- Left Caudate
- Right Caudate
- Left Putamen
- Right Putamen

For regions including the whole brain, lateral ventricles, left caudate, and right caudate, the vendor will supply the absolute baseline volume and the change in volume from baseline using baseline as a reference timepoint. To estimate volume at Visits 5 (Month 3) and 8 (Month 12), BSI volume change will be subtracted or added to the baseline volume depending on the region.

For the whole brain and caudate areas, a positive BSI value means a decrease in volume (also known as atrophy), thus, the estimated volume at follow-up will be calculated as follows:

$$\text{Volume}_{\text{Follow-up}} = \text{Volume}_{\text{baseline}} - \text{Volume Change}_{\text{Follow-up}}$$

In addition, volume and volume change for the left and right caudate volume will be reported separately. To estimate total caudate volume, the left and right volume and volume change estimates will be summed.

For the lateral ventricles, a positive BSI value means an increase in volume (also known as expansion), thus, the estimated volume at follow-up will be calculated as follows:

$$\text{Volume}_{\text{Follow-up}} = \text{Volume}_{\text{baseline}} + \text{Volume Change}_{\text{Follow-up}}$$

The BSI is unsuitable for use with the putamen because it lacks a distinct boundary. For the left and right putamen, absolute volumes at baseline and post-baseline time points will be provided directly by the vendor. To estimate total putamen volume, the left and right volume estimates will be summed. To estimate volume change from baseline over time volume at follow-up will be subtracted from the baseline volume, as follows:

Volume Change Follow-up = Volume _{baseline} - Volume Follow-up

A positive putamen volume change will indicate a volume decrease at follow-up, i.e. atrophy, and vice versa.

Additionally, the striatum volume, which is the sum of the total caudate and total putamen volumes, and the change in striatum volume over time will be reported.

Endpoint QC is performed by trained image analysts for all vMRI endpoints. A Pass/Fail grade is assigned after the QC. Only data with a QC flag equal to 'Pass' will be used in the analysis.

3.4.4. Composite Unified Huntington's Disease Rating Scale

The composite Unified Huntington Disease Rating Scale (cUHDRS) is a comprehensive clinical outcome measure specifically designed to assess the progression of HD. It integrates multiple aspects affected by the disease, including motor, cognitive function, and global functional declines, into a single composite score ([Schobel et al. 2017](#)). This cUHDRS aims to provide a more accurate and sensitive evaluation of disease progression compared to individual assessments. The composite score is calculated by combining the individual scores from the above domains into a single metric. This approach aims to provide a more holistic view of the patient's clinical status and disease progression. It involves integrating the following components from the UHDRS ([Huntington Study Group, 1996](#)):

- Total Motor Score (TMS): Assesses motor function.
 - The motor section of the UHDRS assesses motor features of HD with standardized ratings of oculomotor function, dysarthria, chorea, dystonia, gait, and postural stability. The total motor impairment score is the sum of all the individual motor ratings, with higher scores indicating more severe motor impairment than lower scores. There are 15 items with 31 motor sub-items (each rated from 0 to 4)/score range 0-124.
- Symbol Digit Modalities Test (SDMT) and Stroop Word Reading (SWR): Evaluate cognitive function.
 - Both SDMT and SWR are used to assess cognitive operations. Results for SDMT are scored on the number of correct responses in 90 seconds; cognitive tasks do not have a set maximum score. The SWR results are reported as the raw number of correct answers given in a 45-second period. Higher scores indicate better cognitive performance.
- Total Functional Capacity (TFC): Measures global functional capacity.
 - The functional capacity portion of the UHDRS consists of 5 items (score range 0-13) assessing how people with HD manage their work, finances, domestic chores, activity of daily living, and their care arrangements. The TFC score is the sum of all the individual functional capacity ratings, with higher scores indicating a better function (0 representing the poorest function).

The cUHDRS score will be calculated as:

$$cUHDRS = \left[\left(\frac{TFC - 10.4}{1.9} \right) - \left(\frac{TMS - 29.7}{14.9} \right) + \left(\frac{SDMT - 28.4}{11.3} \right) + \left(\frac{SWR - 66.1}{20.1} \right) \right] + 10$$

where cUHDRS decreases as the disease progresses.

3.4.5. Multicenter Study

No adjustment or stratification for site will be performed. Data from all centers will be pooled for all analyses.

3.4.6. Study Analysis Visit

Study analysis visits during the study will be derived as listed in [Table 2](#), based on study days from the randomization date. This window applies to scheduled, unscheduled, or early termination visits. The analysis visit number for each visit, including scheduled, unscheduled, repeat, and early termination/end of study visits, will be re-mapped. Study analysis visits will be used in all by-visit summaries for both efficacy and safety assessments wherever appropriate.

Table 2: Analysis Visit Windows

Analysis Visit	Target Study Day	Analysis Window (Study Day Range)
Visit 3 (Month 1)	30	16-45
Visit 4 (Month 2)	60	46-75
Visit 5 (Month 3)	90	76-120
Visit 6 (Month 6)	180	151-210
Visit 7 (Month 9)	270	241-300
Visit 8 (Month 12)	360	331- (last dose of study drug + 30 days)

For a given subject, if multiple assessments are within the same analysis window, the assessment at the scheduled visit will be used for the analysis; if the scheduled assessment is not available, the one closest to the scheduled study day and with non-missing value will be used for the analysis at that visit. In case of equal number of days to the scheduled visit date, the later assessment with non-missing value will be used for the analysis at that visit. In summary, the assessment to be used for the analysis is determined by the following order:

- 1) The assessment at the scheduled visit
- 2) The assessment closest to the target study day
- 3) The latter assessment, if ≥ 2 observations are equally close to the target study day

Any assessments occurring beyond the last dose of study drug + 30 days will be excluded from the analysis.

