3.7. Unscheduled Visits

Unscheduled visits are permitted at the investigator's discretion.

At minimum, adverse events and concomitant medications data must be collected at all unscheduled visits. Unscheduled visits may also include any of the following assessments, at the investigator's discretion:

- Physical examination
- Body weight
- Vital signs
- Pregnancy test
- Dispense study drug (if applicable)
- Drug accountability
- ECG

[REDACTED]

- Blood HTT protein
- Plasma NfL

- Clinical laboratory assessments
- UHDRS Part II (SDMT only)
- UHDRS Part V
- UHDRS Part VI

[REDACTED]

- C-SSRS

In addition, if a subject is intended to enroll in the Phase 2 long-term extension study (Study PTC518-CNS-004-HD), but that study is not yet locally approved by regulatory and/or ethics authorities, the subject may continue within this study attending unscheduled visits approximately every 3 months prior to the end of study visit in order to ensure study treatment is not interrupted and to continue to assess safety parameters. Upon local approval of the Phase 2 long-term extension study (PTC518-CNS-004-HD), the subject will return for the End of Study Visit and will transition into the long-term extension study.

Table 4: Study Design and Schedule of Assessments

	Screening	Baseline		Treatment Period						Safety Follow-Up			Notes	
		Month -57 to -8	Days -22 to -1	Day 1	Month 1	Month 2	Month 3	Month 6	Month 9	Month 12 /EOS/ EOT /ET	Month 13	Month 16	Month 18	
Study Month														The Safety Follow-up visits must be performed for all subjects following either the EOT or ET visit.
Visit	1	2		3	4	5	6	7	8	9	10	11		
Window (days)				±7	±7	±7	±7	±7	±7	±7	±7	±7		
Informed consent	X													
Inclusion/Exclusion	X	X	X											
Medical history	X													
Physical examination	X						X	X	X	X				A complete physical exam will be performed at Visit 1 (Screening) and Visit 8/ET. A brief physical examination, including a neurological examination, will occur at all other timepoints.
Demographics	X													
Concomitant medications	X	X	X	X	X	X	X	X	X	X	X			
Body weight and height		X		X	X	X	X	X	X					Height will be collected at Baseline only.
Vital signs	X		X	X	X	X	X	X	X	X				

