Adverse events	X	X	X	X	X	X	X	X	X	X	X	X	Safety follow-up at Visit 9 may be done by telephone/telehealth. Information about AEs will be collected from the signing of consent through 6 months after the last dose of study medication.
C-SSRS	X	X		X	X	X	X	X	X				The “Baseline” version of the C-SSRS version will be used at Screening and Baseline. The “Since Last Visit” version of the C-SSRS will be used at all other timepoints.

Abbreviations: AE, adverse event; CAG, cytosine-adenine-guanine; CSF, cerebrospinal fluid; C-SSRS, Columbia Suicide Severity Rating Scale; ECG, electrocardiogram; eCRF, electronic case report form; EOS, end of study; EOT, end of treatment; ET, Early Termination; FuRST 2.0, Functional Rating Scale; HCG, human chorionic gonadotropin; HTT, huntingtin (protein); HTT, huntingtin (gene); IS, Independence Scale; NfL, neurofilament light chain; PBA-s, short form of the Problem Behaviors Assessment; PIN_{HD}, normed version of the Huntington’s disease prognostic index; PK, pharmacokinetics; SDMT, Symbol Digit Modalities Test; TFC, Total Functional Capacity; TMS, Total Motor Scale; [REDACTED]; TUG, Timed Up and Go; UHDRS, Unified Huntington’s Disease Rating Scale; vMRI, volumetric magnetic resonance imaging; WOCBP, women of childbearing potential

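### The planned C-SSRS tables can omit a 'Yes' from an unscheduled or early-termination visit that shares a window with a scheduled one, and no any-time count is planned

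*SAP*

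**What the plan says.** SAP 3.4.6 defines windows around target days and assigns each assessment to one of them: "This window applies to scheduled, unscheduled, or early termination visits". Where a window holds more than one, "if multiple assessments are within the same analysis window, the assessment at the scheduled visit will be used for the analysis". Only if there is no scheduled assessment does the one nearest the target day count. On scope, the section says: "Study analysis visits will be used in all by-visit summaries for both efficacy and safety assessments wherever appropriate".

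SAP 6.8 plans two C-SSRS tables. The first counts subjects answering 'Yes' to items or categories, "descriptively by visit and treatment group. These C-SSRS items and categories are as follows". The second gives "the shift from baseline to each post-baseline visit in suicidal ideation and behavior". A by-subject listing is also planned. No row covers the whole post-baseline period, and no shift goes to the worst post-baseline category.

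Protocol 3.7 leaves unscheduled visits to the investigator's discretion. "Unscheduled visits may also include any of the following assessments", it says, and the C-SSRS is on the list that follows. In Protocol Table 4 the Baseline form is used at Screening and Baseline, and the 'Since Last Visit' "version of the C-SSRS will be used at all other timepoints".

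SAP 3.2 says of mapping unscheduled and early-termination visits to scheduled ones: "This approach ensures that all relevant data is included in the analysis".

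**The concern.** Safety is a primary objective and the C-SSRS is a named safety endpoint. For this instrument a single positive answer is the information of interest, so a rule that picks one assessment per window can remove exactly what the table is meant to show. A subject who reports ideation on treatment can be tabulated as having none.

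There is also a simpler gap. Even if nothing were discarded, percentages at each visit do not tell the reader how many subjects had any ideation or behavior during treatment. That count is the natural one for comparing arms on suicidality, and the plan does not produce it.

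**Working it through.** The plan states no figure for this point, so there is nothing to reproduce. The check applies the SAP 3.4.6 rule to its own windows.

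**1. One subject.** Suppose the scheduled Month 3 C-SSRS is on Day 88 and all 'No', and an early-termination C-SSRS on Day 110 has a 'Yes' for ideation. Both days lie in the Month 3 window (76 to 120). The scheduled assessment is used, so Month 3 is tabulated as 'No'. Table 4 shows no C-SSRS at the follow-up visits in Months 13, 16 and 18.

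**2. When the rule bites.** Assume scheduled visits fall on the target days. Place one extra 'Yes' on each other day from 2 to 360, which gives 359 − 6 = 353 possible days. The Month 12 window, which runs to 30 days after the last dose, is cut at Day 360 for this count.

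| Window (days) | Target day | Days before target | Days after target |
|---|---|---|---|
| Month 1 (16–45) | 30 | 14 | 15 |
| Month 2 (46–75) | 60 | 14 | 15 |
| Month 3 (76–120) | 90 | 14 | 30 |
| Month 6 (151–210) | 180 | 29 | 30 |
| Month 9 (241–300) | 270 | 29 | 30 |
| Month 12 (331–360) | 360 | 29 | 0 |
| Total | | 129 | 120 |

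Days in no window: 2–15, 121–150, 211–240 and 301–330, which is 14 + 30 + 30 + 30 = 104. Check: 129 + 120 + 104 = 353.

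- *Subject who attends every scheduled visit, with the 'Yes' at an unscheduled visit.* On all 129 + 120 = 249 in-window days the scheduled 'No' is used instead. The other 104 days fall in no window, which is a separate mechanism. None of the 353 reaches a C-SSRS table.
- *Subject who leaves early, with the 'Yes' at the early-termination visit.* Before the target day there is no competing scheduled value, so the 'Yes' is kept: 129 days (37%). After the target day it loses to the scheduled value: 120 days (34%). The remaining 104 days (29%) fall in no window.

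These are counts of calendar days, not probabilities. They show when the rule applies, not how often it will.

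**3. Recall period.** The form used at every post-baseline visit asks about the time since the last visit. Ideation reported at an unscheduled visit and then resolved need not be recorded at the next scheduled one. Ideation that persists or recurs would be.

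**4. Size per subject.** The sample-size sections give about 24 subjects per active arm in each of two stages: 24 × 2 = 48. One omitted subject is 1/48 = 2.1 percentage points. For placebo, 36 × 2 = 72 and 1/72 = 1.4 points. If the optional 18 extra subjects per stage all joined one dose, (24 + 18) × 2 = 84 and 1/84 = 1.2 points.

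**5. By-visit against any-time.** Suppose, as an illustration only, that one subject in an arm of 48 is positive at each of five visits. Each visit shows 2.1%. If it is the same subject throughout, the any-time figure is 1/48 = 2.1%; if five different subjects, it is 5/48 = 10.4%. The planned item-count table looks the same in both cases.

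**The case against.** The strongest reply is that the loss is conditional and the information is not gone. An unscheduled or early-termination value is dropped by this rule only when a scheduled one shares its window. Listings keep every C-SSRS result. An event recorded as an AE enters the TEAE tables of SAP 6.1, which count each subject once up to 30 days after the last dose and use no visit windows. The DSMB reviews safety data unblinded. The safety scope is qualified by 'wherever appropriate', SAP 3.4.8 says in general terms that all available data are analysed and tabulated, and the table shells are in a separate document. All of this is true and limits the point. It does not remove it: no text names a C-SSRS exception, the general sentence in 3.4.8 does not override a specific selection rule, and listings give no rate by arm.

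Several stronger readings are tempting, and the documents do not support them:

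- *Any suicidality reported outside scheduled visits vanishes from the tables.* Under this rule it does not; see the 129 early-termination days on which the value is kept.
- *Unscheduled visits are mostly prompted by a concern, so the rule removes the most abnormal values.* Protocol 3.7 says only that they are at the investigator's discretion, and one stated use is routine bridging to the extension study.
- *The arm comparison is biased.* The rule is the same in every arm, and nothing shows a direction.
- *Laboratory and ECG summaries fail in the same way.* Protocol 9.3.2 plans on-study laboratory abnormalities by worst grade, SAP 3.5 declares no change to the planned analysis, and SAP 6.6 analyses the maximum post-baseline QTcF. Whether SAP 6.2 carries out the worst-grade plan is a different question.

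**Conclusion.** The concern holds in a limited form. Followed as written, SAP 3.4.6 and 6.8 together can tabulate a subject with on-treatment ideation or behavior as 'No', and they produce no count of subjects with any such report. Within-arm suicidality can therefore be understated in the planned C-SSRS tables.

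The size cannot be estimated, because the documents give neither a C-SSRS positivity rate nor an expected number of unscheduled or early-termination assessments. Per omitted subject it is about 2.1 percentage points with 48 subjects in an arm, or 1.2 to 1.4 points in the larger groups. The day counts assume that scheduled visits fall on target days.

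This is a reporting gap for a named safety endpoint. It does not affect the efficacy analyses, and it gives no ground for saying that one arm would look safer than another.

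**What to change.** In SAP 6.8 add two summaries by treatment group:

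- for each C-SSRS item and category, the number and percentage of subjects with a 'Yes' at any time post-baseline;
- a shift from baseline to the worst post-baseline category, with the three categories already defined there.

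Both should use all scheduled, unscheduled and early-termination assessments from first dose to 30 days after last dose. In SAP 3.4.6 state that scheduled-first selection does not apply to them. Because they do not depend on windows, they also pick up assessments on days that belong to no window, and the repeated unscheduled visits of subjects waiting for the extension study within that period. The by-visit tables can stay as they are. No change to the laboratory or ECG-interpretation summaries is needed for this point.

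The cost is a few sentences and minor programming, with no new data. Reported rates may rise slightly in all arms.
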